7.7 Duration of follow up

- If a patient discontinues treatment due to progression within 5 years of registration, submission of an event monitoring form is required every 6 months thereafter until death or a maximum of 5 years post-registration.
- If a patient discontinues treatment due to reasons other than progression or death within 5 years of registration, submission of an event monitoring form is required every 3 months until progression then every 6 months thereafter until death or a maximum of 5 years post-registration.
- If a patient is deemed ineligible after receiving treatment, all study-related materials including biospecimen data up until the point of confirmation of ineligibility must be submitted. The patient will proceed to event monitoring phase per [Section 4.2](#) of the protocol.
- If a patient does not receive treatment, On-study material and the End of Active Treatment/Cancel Notification Form must be submitted. No further follow-up information is necessary.

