13.8 Ineligible

A patient is deemed *ineligible* if after registration, it is determined that at the time of registration, the patient did not satisfy each and every eligibility criteria for study entry. The patient may continue treatment off-protocol at the discretion of the physician as long as there are no safety concerns, and the patient was properly registered. The patient will go directly to the event-monitoring phase of the study (or off study, if applicable).

- If the patient received treatment, all data up until the point of confirmation of ineligibility must be submitted. Event monitoring will be required per Section 18.0 of the protocol.
- If the patient never received treatment, on-study material must be submitted. Event monitoring will be required per Section 18.0 of the protocol.

13.9a Major violation

A patient is deemed a *major violation*, if protocol requirements regarding treatment in cycle 1 of the initial therapy are severely violated that evaliability for primary end point is questionable. All data up until the point of confirmation of a major violation must be submitted. The patient will go directly to the event-monitoring phase of the study. The patient may continue treatment off-protocol at the discretion of the physician as long as there are no safety concerns, and the patient was properly registered. Event monitoring will be required per Section 18.0 of the protocol.

13.9b Cancel

A patient is deemed a *cancel* if he/she is removed from the study for any reason before any study treatment is given. On-study material and the End of Active Treatment/Cancel Notification Form must be submitted. No further data submission is necessary.

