16.11 Primary endpoint

The primary endpoint is the confirmed tumor response rate defined as 100% times the number of eligible patients who has started lenvatinib and whose objective tumor status was a CR or PR on 2 consecutive evaluations at least 4 weeks apart (using RECIST v1.1 criteria) divided by the number of eligible patients who has started lenvatinib.

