16.22 Definitions and analyses of secondary clinical endpoints

- Safety profile of lenvatinib
- Duration of tumor response
- Progression-free survival time
- Overall survival time
- Patient reported quality of life (QOL) using EQ-5D, and FACT-G

16.221 Safety profile of lenvatinib

All adverse events will be graded using the NCI CTCAE Version 4.0. For each type of adverse event classified as either possibly, probably, or definitely related to study treatment, the proportion of patients experiencing a severe (grade 3 or higher) adverse event will be noted per cycle. The maximum grade for each type of adverse event will be recorded for each patient, and frequency tables will be reviewed to determine adverse event patterns.

16.222 Time to event distributions

Time to event distributions will be estimated using the Kaplan-Meier method

16.2221 Duration of response

Duration of response is defined for all patients whose tumor met the criteria of CR or PR (using the RECIST criteria) as the date at which the patient's objective status is first noted

to be either a CR or PR to the date progression is documented.

16.2223 Progression-free survival

Progression-free survival is defined as the time from registration to documentation of disease progression. If a patient dies without a documentation of disease progression, the patient will be considered to have had tumor progression at the time of their death unless there is sufficient documented evidence to conclude no progression occurred prior to death.

If the patient is declared to be a major treatment violation, the patient will be censored on the date the treatment violation was declared to have occurred. In the case of a patient starting treatment and then never returning for any evaluations, the patient will be censored for progression on Day 1 post treatment.

16.2224 Overall survival time

Overall survival time is defined as the time from registration to death due to any cause.

16.2225 Patient reported quality of life (QOL) using EQ-5D, and/or FACT-G

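### PFS leaves out deaths documented as progression-free without saying how they are analysed, and duration of response has neither a death event nor a censoring rule

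*Combined protocol and SAP*

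**What the plan says.** All references are to the combined protocol and SAP.

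- **Estimation (16.222).** "Time to event distributions will be estimated using the Kaplan-Meier method". No competing-risk method is named.
- **PFS (16.2223).** The clock runs from registration to documented progression. Death without documented progression counts as progression at the date of death, "unless there is sufficient documented evidence to conclude no progression occurred prior to death". Nothing says what evidence is sufficient, who judges it, or how the excepted patient enters the analysis. The section has two explicit censoring rules. For a major treatment violation, "the patient will be censored on the date the treatment violation was declared to have occurred"; a patient who starts treatment and never returns for evaluation is censored on Day 1. There is no rule for a patient alive and progression-free at the last assessment.
- **Duration of response (16.2221).** "Duration of response is defined for all patients whose tumor met the criteria of CR or PR", by RECIST, running from the date the status is first noted "to be either a CR or PR to the date progression is documented". Death is not mentioned, and neither is censoring.
- **Response in the primary endpoint (16.11).** A responder is a patient "whose objective tumor status was a CR or PR on 2 consecutive evaluations at least 4 weeks apart".
- **Overall survival (16.2224).** Every death counts, whatever the cause.
- **Follow-up (7.7).** For patients who stop treatment for reasons other than progression or death, "submission of an event monitoring form is required every 3 months until progression then every 6 months thereafter until death" or until 5 years after registration.

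**The concern.** PFS is ordinarily read as time alive without progression, so a death ends it. Here some deaths do not, and the group is defined by a judgement with no stated standard. Two statisticians could follow 16.2223 faithfully and report different curves from the same data.

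The deaths most open to the exception are toxic and intercurrent ones, because those are the deaths for which a lack of progression can be documented. Section 16.32 counts early death from toxicity or from other causes as treatment failure, but for the response rate only, so it does not settle PFS.

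Duration of response has the wider gap. The PFS default, under which most deaths count, is not carried over to it.

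The results will also be read beside published lenvatinib figures. Section 1.232 cites the phase 3 thyroid cancer trial with a hazard ratio that covers both progression and death. A PFS estimate that drops some deaths is not like for like.

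**Working it through.** **The plan's own figures.** None is given for PFS or duration of response. The only design calculation is the two-stage table in 16.13. Exact binomial summation for the rule (0 of 6 stops; 4 or more of 23 is promising) gives 0.149 at a 10% response rate and 0.852 at 30%, matching the stated 0.15 and 0.85. Neither endpoint at issue enters that calculation.

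**Inputs for the PFS illustration.**
- n = 23, from 16.122.
- Median of the reported curve: 12 months, an assumption. It lies between the 9.0 and 18.3 months quoted in 1.232 for other tumours.
- k = number of excepted deaths expected among the 23 patients if all are followed to a first event. The documents give no figure; k = 1 to 3 is assumed.
- Excepted deaths are taken as censored, which is a reading of 16.222 and not stated text.

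**Formula.** Let L = ln2/12 be the progression hazard and M the hazard of an excepted death. Setting M/(L+M) = k/23 gives M/L = k/(23−k): 1/22 = 0.045 for k = 1 and 3/20 = 0.15 for k = 3. The reported curve is S(t) = exp(−Lt). The progression-or-death curve is exp(−(L+M)t) = S(t)^(23/(23−k)). The overstatement is

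Gap(t) = S(t) − S(t)^(23/(23−k)).

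**At 12 months, S = 0.5.**
- k = 1: 0.5 − 0.5^(23/22) = 0.5 − 0.4845 = 0.0155, about 1.6 points.
- k = 3: 0.5 − 0.5^(23/20) = 0.5 − 0.4506 = 0.0494, about 4.9 points.

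**Other times and timing assumptions (percentage points).** The second pair of rows allows no excepted death before the first re-evaluation at 8 weeks (1.84 months), with the same expected k.

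| Timing of excepted deaths | k | 3 months | 12 months | 24 months |
|---|---|---|---|---|
| Constant hazard | 1 | 0.66 | 1.55 | 1.53 |
| Constant hazard | 3 | 2.16 | 4.94 | 4.69 |
| None before 8 weeks | 1 | 0.29 | 1.47 | 1.57 |
| None before 8 weeks | 3 | 0.95 | 4.74 | 4.88 |

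Simulated trials of 23 patients (6,000 runs, Kaplan-Meier computed both ways, constant hazard) gave 1.58 and 4.91 points at 12 months for k = 1 and 3.

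**Median.** For a reported median m, the progression-or-death median is m(23−k)/23, shorter by m × k/23. For m = 9 this is 0.39 months (k = 1) and 1.17 (k = 3); for m = 18 it is 0.78 and 2.35.

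**Scale.** The standard error of a survival estimate of 0.5 in 23 patients is √(0.25/23) = 0.104, or 10.4 points. The 12-month gap is about 15% of that for k = 1 (1.55/10.4) and just under half for k = 3 (4.94/10.4).

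**Major violators.** They are defined by cycle 1 treatment (13.9a), so they are censored near time zero. If one such patient has h times the hazard of the others, censoring shifts S = 0.5 by 0.5 − (22 × 0.5 + 0.5^h)/23: 0 points for h = 1, +1.1 for h = 2, −0.9 for h = 0.5.

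**Duration of response.** Direction only. If deaths in response are censored, the estimate lengthens. The k above counts excepted PFS deaths among 23 patients. That is a different group from all deaths without progression among responders, who would number about 7 at the 30% target rate (0.30 × 23 = 6.9). The documents give no rate for that group.

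**The case against.** The case for leaving this alone is substantial. Both endpoints are secondary summaries in a single-arm study, with no power or decision attached. The number of excepted deaths and the median are assumptions, and the illustrated PFS shift is well inside random error. The PFS default does count deaths, and 11.45 classes disease-related global deterioration without objective progression as progressive disease, which narrows the exception further. Overall survival already counts every death.

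This limits the size of the point and does not remove it. Neither the default nor 11.45 reaches toxic or intercurrent deaths. Random error is no defence for a shift of fixed direction that can be removed by wording.

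A reader might infer more than the documents support:

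- *That the plan censors excepted deaths.* It does not say so. The overstatement is conditional on that reading.
- *That censoring major violators is an error of the same kind.* It is an explicit, prespecified choice, confined to cycle 1 violations serious enough to put evaluability in doubt. Its effect is about one point either way, of unknown sign. These patients do go on to event monitoring, but 4.2 and 7.7 cap that at 5 years and schedule no imaging, so their progression dates would be irregular.
- *That unconfirmed responders enter duration of response.* Section 16.2221 does not use the word confirmed, but 11.33 requires a scan 4 weeks after a first CR or PR, and dating a confirmed response from its first observation fits the text. This is a wording gap.
- *That duration of response is overstated by a stated number of months.* No input in the documents supports such a figure.

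**Conclusion.** The point stands for deaths. Section 16.2223 removes deaths documented as progression-free from the PFS event and leaves both the evidence standard and the handling open. Section 16.2221 gives duration of response no death event and no censoring rule. No other section supplies the missing rules.

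If these deaths are censored, both estimates move upward. For PFS the illustrated size at 12 months is 1.6 points for one such death and 4.9 for three, given 23 patients, a 12-month median and constant hazards. Delaying the excepted deaths past 8 weeks barely changes the 12-month figures. A competing-risk analysis would give a different quantity, to which these figures do not apply.

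This should be corrected before analysis. A reader might infer that it weakens the trial's main conclusion. It does not: the primary endpoint, stage rules, sample size and overall survival do not use either definition.

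**What to change.** Change the wording of 16.2221 and 16.2223:

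1. **PFS:** registration to the first of documented progression or death from any cause.
2. **Duration of response:** in responders confirmed under 16.11, from the first CR or PR to the first of documented progression or death from any cause.
3. **Censoring for both:** patients alive without progression are censored at the last disease assessment.
4. **If the present exception is kept:** report it only as a sensitivity analysis, described as what it is (excepted deaths censored, other deaths counted as progression), and state the evidence required. It should not be called time to progression, because it still counts deaths of uncertain status as progression.
5. **Optional:** a PFS sensitivity analysis that follows major violators through event monitoring instead of censoring them, noting the 5-year limit and the absence of scheduled imaging.

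The cost is wording. Progression and death are already collected under 4.2 and 7.7, and the confirming scan is already required by 11.33. Reported PFS and duration of response may come out slightly less favourable. No visit, scan, patient or decision rule changes.

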1.3 Rationale

Based on information presented above, agents implicated in inhibition of angiogenesis have been for long postulated as possible therapies for pheochromocytomas and paragangliomas (Jimenez, Cabanillas et al. 2009; Joshua, Ezzat et al. 2009; Ayala-Ramirez, Chougnat et al. 2012; Jimenez, Rohren et al. 2013). To date, however, no clinical trials of tyrosine kinase inhibitors have been undertaken in pheochromocytoma/paraganglioma.

In order to more rigorously assess the efficacy of tyrosine kinase inhibition in pheochromocytoma/paraganglioma, we plan to evaluate the tyrosine kinase inhibitor lenvatinib in these diseases in a phase II trial. Both patients with secretory and non-secretory pheochromocytoma or paraganglioma will be permitted in the study as there is no substantial evidence to suggest that these tumor types are expected to have a differential response to lenvatinib—but we will examine this possibility in exploratory analyses as feasible.

It is also not known whether patients with prior exposure to tyrosine kinase inhibitors may have differential rate of response to lenvatinib compared to patients without such prior exposure. However, accumulating clinical evidence and experience in renal cell carcinoma and in thyroid cancer would suggest that tyrosine kinase inhibitors in general appear active even after prior exposure to anti-angiogenic therapy. Moreover, the patient response described in Figure 2 was observed in a patient who had previously received both CVD, and later, pazopanib therapy. As a result, and in consideration of the rarity of pheochromocytoma and paraganglioma requiring therapy as outlined in the clinical trial, we feel that there is greater disadvantage than advantage to developing independent patient cohorts based upon presence/absence of prior tyrosine kinase inhibitor therapy.

In assessing safety and efficacy of lenvatinib in patients with pheochromocytoma or paraganglioma, and given the wide range and seriousness of reported side effects, we plan to incorporate QOL data while treating our patient cohort in correlation with response outcomes. QOL data will be collected at baseline and every two months on therapy. We propose to use EQ-5D-5L descriptive questionnaire system designed by EuroQol group as well as FACT-G (Functional Assessment of Cancer Therapy-General).

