1.4 Hypotheses

Hypothesis 1: Lenvatinib treatment of patients with advanced malignant pheochromocytoma and paraganglioma may lead to attenuated tumor growth and/or tumor regression (as defined by RECIST criteria – see [Section 11.0](#)).

Hypothesis 2: Lenvatinib-induced changes in plasma and urinary catecholamine and/or metanephrine levels in patients with advanced, catecholamine secreting pheochromocytoma and paraganglioma may be observed and be predictive of patient objective response to lenvatinib therapy (per RECIST criteria – see [Section 11.0](#)).

Hypothesis 3: Somatic mutational status (presence of SDHD, SDHB, RET, VHL, neurofibromatosis type-1 in archival tumors) may predict response to lenvatinib therapy.

Hypothesis 4: Germline mutational status (detection of SDHD, SDHB, RET, VHL, neurofibromatosis type-1 in patient's PBMCs) may predict response to lenvatinib therapy.

Hypothesis 5: There is no significant deleterious net change in patient reported quality of life during lenvatinib therapy.

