2.2 Secondary objectives

- 2.21 To determine progression-free survival (PFS)
- 2.22 To determine overall survival (OS)
- 2.23 To determine duration of tumor response
- 2.24 To determine safety and tolerability of lenvatinib
- 2.25 To assess patient reported quality of life using EQ-5D-5L and FACT-G

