⁸ AST, alk phos, total bilirubin (direct if TBili is elevated), creatinine (and calculated creatinine clearance), albumin, glucose, calcium (Ca), sodium (Na), potassium (K), magnesium (Mg), phosphorus (P), uric acid, LDH,

⁹ Urinalysis for protein, glucose, blood

¹⁰ Only if not performed previously (optional); can be performed anytime during study. Testing should include SDHD, SDHB, RET, VHL, neurofibromatosis type-1 genes.

Tests and procedures ¹	Window:				Active Treatment			End of Treatment
		≤28 days prior to registration	≤14 days prior to registration	≤7 days prior to registration	Cycle 1		Prior to Day 1 of subsequent cycles ³	
		D1	D3	D10 ²	Every 2 months			
PET-CT or CT (Chest, Abdomen and pelvis), or MRI abdomen/MRI neck, if needed	X						X	X ¹¹
ECG		X					X ¹²	
2D-ECHO	X							
Blood or Tissue- Analysis performed by Research Lab								
Optional tissue sample for correlatives (see Section 17.0) ¹³				X				
Optional research blood will be collected under IRB 13-005838 ¹⁴		X						
Quality of Life assessment								
Patient Questionnaire Booklet: EQ-5D-5L/FACT-G				X ¹⁵			X	

Cycle = 28 days

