4.2 Event Monitoring/Survival Follow-up

	Event Monitoring Phase ¹				
	q. 3 months until PD	At PD	After PD q. 6 months	Death	New Primary
Event Monitoring	X	X	X	X	At each occurrence

1. If a patient is still alive 5 years after registration, no further follow-up is required.

¹¹ Repeat imaging needed within 4 weeks of documentation of disease recurrence per RECIST (see [Section 11.0](#)).

¹² Only for Cycle 2 and 3

¹³ Request archived tissue if patient has consented to release of tissue.

¹⁴ Contact [REDACTED] for specifics.

¹⁵ Baseline booklet must be completed after patient has consented and prior to first treatment

5.0 STRATIFICATION FACTORS: None**6.0 REGISTRATION PROCEDURES****6.1 Registration****6.11 Mayo Clinic Sites**

To register a patient, access the Mayo Clinic Cancer Center (MCCC) web page and enter the remote registration/randomization application.

The registration/randomization application is available 24 hours a day, 7 days a week. Back up and/or system support contact information is available on the Web site. If unable to access the Web site, call the MCCC Registration Office at [REDACTED] between the hours of 8 a.m. and 5:00 p.m. Central Time (Monday through Friday).

The instructions for the registration/randomization application are available on the MCCC web page [REDACTED] and detail the process for completing and confirming patient registration. Prior to initiation of protocol treatment, this process must be completed in its entirety and a MCCC subject ID number must be available as noted in the instructions. It is the responsibility of the individual and institution registering the patient to confirm the process has been successfully completed prior to release of the study agent. Patient registration via the registration/randomization application can be confirmed in any of the following ways:

- Contact the MCCC Registration Office [REDACTED]. If the patient was fully registered, the MCCC Registration Office staff can access the information from the centralized database and confirm the registration.
- Refer to "Instructions for Remote Registration" in section "Finding/Displaying Information about A Registered Subject."

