Descriptive statistics, and scatter plots will form the basis of presentation of these data both overall and by other outcomes (toxicity, response and survival measures). Correlations between the QOL outcomes and other outcome measures will be carried out by standard parametric and non-parametric tests (e.g. Pearson's and Spearman's rho). Comparison between continuous variables will be made with Wilcoxon rank sum tests, Fisher's exact tests will be used to determine differences between categorical variables, and Log-rank test will be used to test differences between time-to-event outcomes.

16.23 Correlative aims:

16.231 For patients with secretory tumors

To examine changes in urinary catecholamine and metanephrine levels during treatment, time series plots of urinary catecholamines and metanephries levels will be constructed (with patient whose tumor responded to treatment in red and patients whose tumor remained stable or progressed in blue) to visually assess trends prior to treatment discontinuation within and between chemistries as well as difference in trends between those whose tumor responded to treatment and those whose tumor did not.

To examine whether lenvatinib-induced changes in urinary catecholamine and/or metanephrine levels during the first cycle of treatment may be associated with objective tumor response, the fold change from baseline levels for each biomarker will be determined. For each biomarker, a plot of the fold change versus response status will be constructed to visually assess differences between those whose tumor

responded to treatment and those whose tumor did not. If feasible, Wilcoxon rank sum tests will be used to examine whether fold changes in a given biomarker during the first cycle of treatment differs between those whose tumor responded to treatment and those whose tumor did not.

- 16.232 To examine associations between tumor response and somatic mutational status in archived tumors, or germline mutational status in patient's peripheral blood mononuclear cells, (presence of SDHD, SDHB, RET, VHL, neurofibromatosis type-1).
For SDHD, SDHB, RET, VHL, neurofibromatosis type-1, a 95% confidence interval for the difference in proportion of patients who have a documented tumor response among those with that particular biomarker present and proportion of patients who have a documented tumor response among those without that particular biomarker present.

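### Hypothesis 5, on quality of life during therapy, has no planned within-patient analysis, and patients who stop treatment between booklets appear to leave no score at stopping

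*Combined protocol and SAP*

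**What the plan says.** Section 1.4 states hypothesis 5: "There is no significant deleterious net change in patient reported quality of life during lenvatinib therapy". Section 2.2 makes QOL a secondary objective: "To assess patient reported quality of life using EQ-5D-5L and FACT-G".

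On collection, section 1.3 says "QOL data will be collected at baseline and every two months on therapy". The section 4.1 calendar has a row for the booklet ("Patient Questionnaire Booklet: EQ-5D-5L/FACT-G") that shows one baseline mark and one on-treatment mark. Footnote 15 fixes the baseline: "Baseline booklet must be completed after patient has consented and prior to first treatment".

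On analysis, section 16.2225 is the whole plan:

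- "Descriptive statistics, and scatter plots will form the basis of presentation of these data both overall and by other outcomes", the other outcomes being toxicity, response and survival;
- "Correlations between the QOL outcomes and other outcome measures will be carried out by standard parametric and non-parametric tests";
- "Comparison between continuous variables will be made with Wilcoxon rank sum tests", with Fisher's exact tests for categorical variables and log-rank tests for time-to-event outcomes.

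The heading of 16.2225 leaves open whether one instrument or both will be used.

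**The concern.** The hypothesis asks whether patients get worse relative to where they started. Each planned analysis either describes scores or relates them to another variable. None estimates change from baseline, although the required baseline booklet makes that possible. With no change estimate, interval or margin, nothing in the plan can confirm or contradict hypothesis 5. Because the hypothesis is worded as an absence of significant change, imprecision would favour it if a non-significant result were taken as support.

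Collection adds to this. Booklets are tied to being on therapy, and several reasons for leaving therapy overlap with what the questionnaire measures. Scores not collected at stopping cannot be recovered at the analysis stage.

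**Working it through.** **1. Question against analysis.** The plan gives no sample size, power, SD, within-patient correlation or margin for QOL, so there is no QOL figure to reproduce. The sample comes from the two-stage design in section 16.12, which does reproduce. An exact binomial calculation (6 then 17 patients, stop at 0 responses, promising at 4 or more) gives 0.149 / 0.368 / 0.585 / 0.748 / 0.852 for declaring promise at response rates of 10 / 15 / 20 / 25 / 30%, against the stated 0.15 / 0.37 / 0.59 / 0.75 / 0.85. QOL therefore rests on 6 to 23 eligible patients.

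Set beside 16.2225, section 16.231 does for biomarkers what is missing for QOL. It defines a fold change from baseline and says that the rank-sum test compares responders with non-responders.

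**2. Who has no score at stopping.** Section 8.2 lists discontinuation for, among others, grade 3 fatigue, grade 3 palmoplantar erythrodysesthesia, and grade 4 diarrhea or nausea/vomiting. FACT-G (Appendix VII) asks about energy, nausea and side effects. A patient who stops before the first on-treatment booklet has only a baseline. One who stops between booklets has nothing after the last one.

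To size this, let a share f leave with an unrecorded change D, while the others change by 0. Then:

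- true mean change = (1 − f) × 0 + f × D = f × D; observed mean change = 0;
- f = 0.10, D = −0.5 SD: −0.05 SD unseen;
- f = 0.30, D = −1.0 SD: −0.30 SD unseen;
- f = 0.40, D = −1.5 SD: −0.60 SD unseen.

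Both f and D are assumptions; the documents give neither.

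**3. What a change analysis could show.** With equal SDs and within-patient correlation ρ (assumed 0.3 / 0.5 / 0.7), the SD of change is √(2(1 − ρ)) in units of the score SD. The 95% half-width for mean change is t(0.975, n − 1) × √(2(1 − ρ)) / √n. For n = 23 and ρ = 0.5 this is 2.074 × 1 / 4.796 = 0.43 SD.

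| Complete pairs | Half-width, ρ = 0.3 / 0.5 / 0.7 | Chance of excluding a 0.5 SD fall if true change is 0 |
|---|---|---|
| 23 | 0.51 / 0.43 / 0.33 SD | 0.49 / 0.63 / 0.84 |
| 12 | 0.75 / 0.64 / 0.49 SD | 0.27 / 0.35 / 0.53 |

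The last column uses a noncentral t at one-sided 0.025 with noncentrality 0.5√n / √(2(1 − ρ)). The 0.5 SD margin is illustrative. At ρ = 0.5, even 23 complete pairs leave an interval of about ±0.43 SD, so a non-significant change does not show absence of harm.

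**The case against.** The strongest reply is that nothing in the plan is actually wrong. QOL is secondary, the objective is only to assess it, overall descriptive statistics could show a fall, adverse events are graded separately, and hypothesis 5 concerns the period on therapy, which on-therapy collection matches. In year 1 imaging is every 8 weeks (section 11.1), so progression found on a scheduled scan should usually fall near a due booklet. An End of Treatment score may be taken after the drug has stopped. A margin with at most 23 patients may well give an inconclusive answer.

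Most of this stands and limits the point. The gap is mainly stopping for toxicity or refusal, and its size is unknown. But descriptive summaries of patients still on therapy carry no rule for answering hypothesis 5, and they do not include scores that were never collected.

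A reader might infer that the rank-sum test will be used to compare baseline with on-treatment scores as if they were separate groups. Section 16.2225 does not say so. After a sentence about presenting QOL by other outcomes, the natural reading is a comparison between patient groups, for which the test is valid. Only if it were used across visits would these simulated figures apply (23 pairs, normal scores, 0.5 SD fall, ρ 0.5 to 0.7, two-sided 0.05): power 0.32 to 0.28, against 0.62 to 0.82 for the signed-rank test, with a true type I error of 0.007 to 0.001. They are not properties of the stated plan.

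**Conclusion.** The point holds as an omission. Hypothesis 5 has no analysis that answers it, and collection as described leaves no score at stopping for some patients, which could make QOL look better than it is. Under the assumed dropout range the unseen mean fall is 0.05 to 0.60 SD.

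A reader might go further and infer that harm is likely to be missed. The documents do not support that. They give no dropout rate, SD, correlation or target change, and do not say that a non-significant test will count as support for the hypothesis.

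The absence of an End of Treatment booklet rests mainly on section 1.3. The calendar row agrees, with two marks where the imaging row has three, but the table is broken in extraction and should be checked against the original.

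This is a cheap improvement to a secondary endpoint. The primary decision rule is unaffected.

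**What to change.** In section 16.2225:

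- name a key score, such as FACT-G total;
- report within-patient change from baseline with a 95% confidence interval at each visit, from a paired or repeated-measures analysis;
- report completion counts and reasons for missing booklets by visit, since a standard repeated-measures model does not by itself remove bias from informative dropout;
- state that rank-sum tests are for comparisons between patient groups, such as responders against non-responders;
- either conclude that there is no deleterious change only if the interval excludes a margin stated beforehand, or label hypothesis 5 as descriptive.

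In section 4.1, add the booklet to the existing End of Treatment visit. Report that score separately as well, because it may be taken after the drug has stopped.

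The cost is one more questionnaire per patient at a visit already scheduled, and a little more analysis. If a margin is chosen, the result may be inconclusive.
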